1.0 OBJECTIVES AND ENDPOINTS

| Objectives | Endpoints/ Measurements |
|---|--|
| Primary Objective | |
| To observe the effect of various cannabinoid-containing products on motivation. | Change in average motivation score by 1 point as measured by a 10-point visual analogue rating scale (VAS) collected between the cannabinoid products and placebo use sessions. |
| Secondary Objective | |
| To observe the effect of cannabinoid products on energy level, focus, and appetite. | Change in average score by 1 point as measured by a 10-point visual analogue rating scale (VAS) between the cannabinoid products and placebo use sessions. |
| Exploratory Objective | |
| To observe changes in overall symptoms and quality of life. To identify improvements for future participant centered study designs using participant feedback. | Changes in overall symptoms and quality of life to be assessed based on MEFA questionnaire responses. Evaluation of study participant experiences based on the experience survey. This may include design and use of app-based data collection tools. |

2.0 INTRODUCTION: BACKGROUND INFORMATION & SCIENTIFIC RATIONALE

2.1 Introduction/Rationale for Development

Tetrahydrocannabivarin (THCV) is a rare cannabinoid and is a homologue of THC that differs only in the length of the alkyl side chain (3C vs 5C, respectively). Pre-clinical and clinical trials have shown that THCV has medical potential as a neuroprotectant, anti-inflammatory, anti-anxiety, and most notably as a therapeutic to improve glycemic control in type 2 diabetic patients.

Several THCV products are available in states with recreational cannabis. Anecdotal reports from adult cannabis users indicate that THCV provides an energizing, focusing and euphoric high—while still creating a lucid, uplifting experience. Additionally, unlike THC-dominant products, THCV was not reported to increase appetite. Other anecdotal comments referring to increased ability to focus for long periods of time and being more active were common.

Given anecdotal evidence, which shows that THCV is activating and improving focus, this provides rationale and justification to conduct a clinical research study to further test and

understand whether THCV improves motivation, focus, level of energy, and does not stimulate appetite in healthy adults.

2.2 Overview of and Rationale for the Study Design

The rationale for this study is to determine the effect of a consumer-grade, state-legal formulation of cannabinoids including Tetrahydrocannabivarin (THCV) on motivation, energy level, focus, and appetite. A consumer-driven, decentralized observational clinical research study is therefore well suited to examine the effect of this formulation in healthy individuals.

We will examine the outcomes in a broad age-range of adults who have chosen to try these products. The study will incorporate participant reported outcomes and surveys collected after each product use session to engage the participant in their typical day-to-day activities. There is no “physician-patient” relationship as part of this research since the participant as a consumer is making the informed choice to take the products and take part in the observational process with self-reported measures. Findings from this study will contribute knowledge toward the design of future cannabis research studies and the improvement of the product formulation.

A new study questionnaire was developed as no existing questionnaire would be able to capture all interest areas of this study in a holistic manner. Other questionnaires related to focus, attention, concentration, fatigue, work, and motivation were assessed and used to support the study questionnaire development.

3.0 SAMPLE SIZE, COHORT CHARACTERISTICS, ELIGIBILITY AND INVOLVEMENT

3.1 Sample Size and Cohort Characteristics

The sample size for this study will be approximately 58 healthy volunteers who meet the eligibility criteria.

3.2 Eligibility

Participants must meet all of the following criteria on screening to be considered eligible to participate in the study:

Inclusion Criteria

1. Healthy adults age \geq 21 years old
2. Work / study / play in an environment that requires focus
3. Able to read and understand English
4. Able to read, understand, and provide informed consent
5. Able to use a personal smartphone device and download Chloe by People Science
6. Able to complete study assessments over the course of up to 14 days
7. Familiar with the use of cannabis and its effects
8. Able to tolerate at least 5mg THC
9. Willingness to abstain from use of any THC containing products during study product use days
10. Willingness to abstain from use of alcohol during study product use days

11. Greater Los Angeles area residents only

Exclusion Criteria

1. Participants who do not have a smartphone and/or internet access
2. Any known adverse effects from taking cannabis
3. Concomitant Therapies: Currently taking medication for ADHD or psychotropic medications
4. Other Illnesses or Conditions: Participants who have the following co-morbidities are excluded:
 - a. History or currently undergoing product use for substance abuse disorders
 - b. Currently pregnant, planning to become pregnant within the next month, or breastfeeding
 - c. Allergies to formulation ingredients
 - d. Current or prior psychotic disorder
 - e. Immunosuppressive product uses, including organ transplant participants, active immunotherapy for cancer product use
 - f. Any condition that is considered by investigator to be a contraindication to cannabis (e.g. specific drug-use interaction, unstable cardiac arrhythmia)

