3.3 Duration of Participation and Overview of What is Expected from Participants

Participants will complete up to a seven week study consisting of screening period, baseline period, up to a 21-day product use period with a total of 9 product use sessions. Screening assessments, baseline questions, product use period questionnaires, adverse event reporting, and end of study experience survey data will be collected. This study will be conducted remotely and will use a web-based data collection platform, Consumer Health Learning and Organizing Ecosystem (Chloe), by People Science where participants will complete study assessments using the Chloe app during the course of the study. Participants will receive the study product during the baseline period. Demographic and medical history data will be collected for the study.

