4.0 STUDY ACTIVITY CALENDAR

Table 4.1 Study Calendar

| Protocol Activities | Screening ^(a) | Baseline ^(b) | Study Duration | | | | | | | | |
|---|--------------------------|-------------------------|---|-----------------------|------------------------------------|---|-----------------------|------------------------------------|---|-----------------------|---|
| | | | Product Use Period 1 ^(c) (Up to 7 Days) | | | Product Use Period 2 ^(c) (Up to 7 Days) | | | Product Use Period 3 ^(c) (Up to 7 Days) | | |
| | Up to Day -14 | Up to Day 14 | Product Use Session 1 | Product Use Session 2 | Product Use Session 3 / Cross-Over | Product Use Session1 | Product Use Session 2 | Product Use Session 3 / Cross-Over | Product Use Session1 | Product Use Session 2 | Product Use Session 3 / End of Study ⁽ⁱ⁾ |
| Informed Consent | X | | | | | | | | | | |
| Medical History | X | | | | | | | | | | |
| Demographics | X | | | | | | | | | | |
| Concomitant Medications | X | | | | | | | | | | |
| Eligibility Confirmation | X | | | | | | | | | | |
| Product Delivery Receipt | | X | | | | | | | | | |
| Randomization ^d (Study Product, THC Only Product, or Placebo Group) | | X | | | | | | | | | |
| MEFA Questionnaire ^e | | X | | | X | | | X | | | X |
| Daily Product Use Survey ^f | | | X | X | X | X | X | X | X | X | X |
| Adverse Event Survey ^g | | | X | X | X | X | X | X | X | X | X |
| Cross-Over ^h (Study Product, THC Only, or Placebo Group) | | | | | X | | | X | | | |
| Experience Survey | | | | | | | | | | | X |

- a. Screening activities to occur within 14 days prior to Baseline (Day -14).
- b. Baseline activities to occur up to 14 days prior to study product use sessions (Day 14).
- c. Study duration to take place up to 21 days total across 7 days maximum within 3 periods.
- d. Participants to be randomized into the Study Product, THC-Only Product, and Placebo groups for each Product Use Period.
- e. MEFA (Motivation, Energy Level, Focus, and Appetite) Questionnaire to be administered during Baseline and at the end of Product Use 3 sessions.
- f. Daily Product Use Surveys to be administered at the end of each product use session.
- g. Any adverse event occurrence to be reported after the product use session.
- h. Participants cross-over into either Study Product, THC-Only Product, or Placebo group upon completion of Product Use Period 1 and 2.
- i. Participants to complete an experience survey at the end of the study.

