9.3 Evaluable Participants

Participants will be considered evaluable for analysis if they complete all assessments in at least two product use sessions within each group of the study.

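### Inclusion criterion 6 tests availability for up to 14 days, but product use and its surveys can run for up to 21, so a person unable to finish Period 3 can be enrolled

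*Combined protocol and SAP*

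**What the plan says.** Section 3.2 makes the listed criteria the eligibility test: "Participants must meet all of the following criteria on screening to be considered eligible". Criterion 6 is the only one that concerns availability over time, and it reads "Able to complete study assessments over the course of up to 14 days".

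The sections on duration give longer figures:

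- Section 3.3 opens with "Participants will complete up to a seven week study" and specifies "up to a 21-day product use period with a total of 9 product use sessions".
- Section 4.0, footnote c: "Study duration to take place up to 21 days total across 7 days maximum within 3 periods". The calendar puts a survey after every session and the MEFA questionnaire at baseline and at the third session of each period. Its other footnotes allow up to 14 days for screening and up to 14 days for baseline.
- Section 6.1 repeats the 21-day maximum for nine sessions, and has participants cross over after three sessions in each of Periods 1 and 2.
- Sections 9.2 and 12.6 give about seven weeks in total.

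Section 9.3 counts participants as evaluable if they "complete all assessments in at least two product use sessions within each group of the study". Sections 9.1 and 9.2 plan for about 50 evaluable out of about 58.

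**The concern.** An eligibility criterion is applied to every candidate. This one states a duration that equals two full-length periods in a three-period crossover. A candidate who can truthfully commit to 14 days and no more satisfies it, and no other criterion asks about the remaining time. Under section 5.3, people who are eligible and consent are registered automatically by the platform, and no later availability check is described.

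What is at stake is avoidable loss late in follow-up. Each participant takes the three products in sequence, and evaluability needs at least two complete sessions on each. A person who stops after Period 2 has no data on whichever product came third in their order, and does not count toward the roughly 50 evaluable completers on which section 9.2 makes the final analysis wait. Losses of this kind could be foreseen at screening if the question asked were the right one.

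**Working it through.** **Inputs.** Criterion 6: 14 days (3.2). Three periods of at most 7 days, with three sessions each (4.0, 6.1). Screening up to 14 days and baseline up to 14 days (4.0). Evaluability: at least two complete sessions per product (9.3). About 58 enrolled and about 50 evaluable (9.1, 9.2). Mean change 1, SD 2, two-sided alpha 0.05, power at least 90%, signed-rank test (9.6).

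**1. Reproduce the stated durations.**
- Product use: 3 x 7 = 21 days. Sessions: 3 x 3 = 9. Both match 3.3 and 6.1.
- Participation: 14 + 14 + 21 = 49 days = 7 weeks, matching 3.3, 9.2 and 12.6.

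The calendar adds up with 21 days. The 14 in criterion 6 is the one figure that does not fit.

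**2. Compare criterion 6 with the time assessments can take.**
- Product use only: 21 - 14 = 7 days uncovered.
- Baseline MEFA and delivery wait included: 14 + 21 = 35 days, so 35 - 14 = 21 uncovered.
- Screening included: 49 days, so 49 - 14 = 35 uncovered.

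At the permitted maximum, 14 days does not cover the assessments on any of these readings.

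**3. When does a 14-day participant fail to be evaluable?** Crossover follows three sessions in each of Periods 1 and 2, so evaluability takes at least 3 + 3 + 2 = 8 sessions and requires Period 3 to be reached.
- Periods 1 and 2 at full length: 2 x 7 = 14 days used, 0 left. Not evaluable.
- Faster use: the documents set no minimum period length or gap between sessions. Assuming one session a day, all nine take as few as 9 days, which is within 14. Evaluable.

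So the outcome depends on the participant's own pace, which the documents leave open up to the 7-day limit.

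**4. Room for loss.** 58 - 50 = 8, and 8/58 = 13.8%. The documents give no expected dropout rate, so the share of any loss due to criterion 6 cannot be estimated.

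**5. Does the power statement change?** On the plan's own inputs the standardised change is 1/2 = 0.5.
- Paired z: n = ((1.960 + 1.282)/0.5)^2 = 42.03, so 43. Paired t: 44.
- Signed-rank under normality (efficiency 3/pi = 0.955): 44/0.955 = 46.1, so 47. At worst-case efficiency 0.864: 44/0.864 = 50.9, so 51.

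Approximate signed-rank power, with illustrative loss rates that are assumptions and not taken from the documents:

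| Evaluable | How reached | Power (normal data) |
|---|---|---|
| 58 | no loss | 95% |
| 50 | 13.8% loss | 92% |
| 46.4 | 20% loss (assumed) | 90% |
| 40.6 | 30% loss (assumed) | 86% |

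At worst-case efficiency, power is 93% with 58 and 89% with 50. The claim of at least 90% with up to 58 therefore stands, and criterion 6 does not enter the calculation. It can matter only through the number of evaluable participants.

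**The case against.** The best case on the other side is that this is one stale line in a document that states the duration correctly everywhere else. The 21 days are a ceiling, participation is remote and app-based, and nine sessions can be completed within 14 days. Consent, obtained during screening and listed before eligibility confirmation in section 6.1, must describe the study's duration (section 12.7), so candidates should learn the real commitment. No calculation in the plan uses the 14-day figure.

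Much of this stands, and it limits what can be claimed. A reader might infer any of the following, none of which the documents support:

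- *That people who cannot finish are in fact being enrolled.* The criterion permits it. Whether it happens depends on who applies and how fast they use the product.
- *That a third of product-use days is at risk.* The plan has nine sessions spread over at most 21 calendar days, not 21 days of use.
- *That a ninth loss breaks the study.* Both 50 and 58 are approximate, and under normality power is still about 90% with about 46 evaluable. Whether losses would be replaced is not stated, so a smaller final sample is not established either.
- *That a non-completer's Period 1 and 2 data are certainly discarded.* Section 9.3 and the complete-case rule in 9.5 point that way, but 9.6 speaks of analysing up to 58 and adds mixed models for correlated observations. The plan is unclear here.
- *That one product loses more data than another.* The product missing is whichever came third, and nothing shows an imbalance.

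What does not stand is the idea that consent makes the criterion harmless. Telling a candidate the duration is not the same as testing for it, and the criterion would still contradict the schedule.

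**Conclusion.** The inconsistency is real and lies in an operative rule. Criterion 6 covers 14 days against a product use phase of up to 21, a shortfall of 7 days, or 21 days once baseline is included. A person available for 14 days only can be enrolled, may be unable to finish Period 3 if they use the full period lengths, and would then fail section 9.3.

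The number affected is unknown. The size of the consequence rests on two things the documents do not give: how many candidates have only 14 days, and how quickly participants use the product. The hypothesis test, sample size and power figures are not themselves altered. This is a minor to moderate consistency correction, worth making before enrolment because it has no effect on people already screened.

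**What to change.** Reconcile criterion 6 in section 3.2 with the schedule stated in sections 3.3, 4.0 and 6.1, so that it asks for ability to complete assessments across all three product use periods (up to 21 days) within participation of up to seven weeks. The schedule itself need not change.

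Check that the pre-screening questionnaire mentioned in section 5.1 and the consent text carry the same figure. Neither is available here, so whether they repeat the 14 days is not known.

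The cost is one line in the protocol, submitted to the IRB as an amendment under section 12.1, plus matching edits elsewhere if needed. A few people who cannot commit to the full duration will be screened out, which may slow enrolment slightly.

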9.6 Statistical Analysis Plan

The primary objective of this study is to determine the impact of Phylos’ study product on motivation as measured by the change in VAS scores from approximately 50 participants. Univariate statistics will be generated to describe the distribution of patient characteristics and outcome data. Continuous variables will be described using means, standard deviations, minimums and maximums while categorical variables will be described using counts and percentages. VAS scores will be compared from baseline pre-product use; and at end of study (post-product use) of the same individuals. We will analyze up to 58 participants to achieve at least 90% power to detect a mean change in VAS scores of 1 point (SD=2) from baseline with a type I error of 0.05 (two-sided) assuming a paired means dependent Wilcoxon Signed-Rank test. We are testing the null hypothesis that there is no difference between pre-product use and post-product use mean VAS scores within study participants. Summary statistics will be generated, and paired differences between pre-product use and post-product use VAS scores will be reported, along with 95% confidence intervals.

Additionally, parametric linear mixed models will be employed to simultaneously account for correlated observations and adjust for confounding variables (Proc Mixed, SAS). Several covariance structures, including compound symmetry and unstructured, will be evaluated by comparing AIC and BIC to identify optimal model fit. Random slope and intercept will also be considered in a similar manner. Patient characteristics (i.e. age and sex) will be included in adjusted models a priori for confounding control. Directed acyclic graphs will be employed to select other potential confounding variables and identify biases during the model fitting process. Large differences will be further examined and may help identify where further calibration of estimation models are needed.

Stratified and interaction analyses will be employed to detect between-subgroup differences in outcomes. Specifically, we will test the difference in VAS score change between Study Product, THC-Only Product, and Placebo groups. Testing of these differences will be conducted by including 2-way product terms between the exposure and covariate of interest in linear mixed modeling. A significant interaction will be defined by an interaction coefficient with a p-value < 0.05.

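### Abstention from own THC and alcohol covers product use days but not the Baseline MEFA, so change from baseline can mix product effect with a difference in background use

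*Combined protocol and SAP*

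**What the plan says.** Two inclusion criteria in section 3.2 govern own use: "Willingness to abstain from use of any THC containing products during study product use days" and "Willingness to abstain from use of alcohol during study product use days". Both are limited to product use days. Participants must also be "Familiar with the use of cannabis and its effects" and able to tolerate at least 5 mg THC.

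On timing, footnote e of the section 4.0 calendar reads "MEFA (Motivation, Energy Level, Focus, and Appetite) Questionnaire to be administered during Baseline and at the end of Product Use 3 sessions". The calendar grid marks the MEFA once at Baseline and then at Session 3 of each of the three periods. Footnote b and section 6.1 give Baseline a window of up to 14 days before the product use sessions. Neither section 4.0 nor section 6.1 attaches an abstention condition, or a record of same-day use, to the Baseline questionnaire.

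On analysis, section 9.6 states that "VAS scores will be compared from baseline pre-product use; and at end of study (post-product use) of the same individuals" and sets the null hypothesis as "no difference between pre-product use and post-product use mean VAS scores within study participants". Its power statement is for a 1-point change from baseline. The section 1.0 table and section 9.1 instead define the outcomes as differences between products, and section 9.6 also plans a between-product test of VAS change.

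**The concern.** A before/after comparison needs both measurements to be taken under the same background conditions, apart from the product. Here the eligibility rules set different conditions. A participant may answer the Baseline MEFA on a day of ordinary cannabis or alcohol use, but has agreed to avoid other THC and alcohol on every day when a later MEFA is due. If own use moves motivation, energy, focus or appetite ratings, its absence on product use days will appear as a change from baseline under each product, placebo included. The pre/post test in section 9.6 has no means of separating that change from a product effect. The same applies to the exploratory changes in symptoms and quality of life drawn from MEFA responses.

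**Working it through.** **Step 1. The two sides of the comparison.**

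| | Baseline MEFA | Later MEFAs |
|---|---|---|
| When | Any time in a window of up to 14 days (4.0, 6.1) | Session 3 of each period (4.0) |
| Product use day? | No | Yes |
| Abstention from other THC and alcohol (3.2) | Not required | Agreed to |

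**Step 2. The plan's own figure.** Inputs from section 9.6: mean change 1 point, SD 2 (read as the SD of the paired change), two-sided alpha 0.05, power at least 90%, signed-rank test, up to 58 analysed. About 50 are expected to be evaluable (9.1, 9.2).

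- Normal approximation: n = ((1.960 + 1.282) × 2 / 1)² = 42.03, so 43.
- Exact paired t: n = 44.
- Signed-rank test, 20,000 simulated trials with normal changes: power about 92% at 50 and about 96% at 58.

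The stated power is reproduced. It presumes that the baseline is not shifted by own use.

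**Step 3. Where the shift acts.** Let a participant's baseline score be B + b, where b is the effect of own use at that moment, and let the score under product k be Y_k.

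- Change from baseline under k: Y_k − B − b. The term b remains.
- Product k minus placebo: (Y_k − B − b) − (Y_placebo − B − b) = Y_k − Y_placebo. The term b cancels, because the calendar has a single Baseline MEFA and each evaluable participant contributes sessions in every group (9.3).

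**Step 4. Illustration of size.** The documents give neither the share of participants affected at baseline (p) nor the mean effect among them (d, in points). In absolute size, the shift in mean change is p × d. If p is assumed to be 0.3 to 0.6, a mean shift of 0.25 point needs d of 0.25/0.6 = 0.42 to 0.25/0.3 = 0.83 point. A shift of 0.5 needs 0.5/0.6 = 0.83 to 0.5/0.3 = 1.67 points. With p or d at zero there is no shift.

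With the SD held at 2, the same simulation gives the chance that the pre/post test rejects when there is no product effect:

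| Assumed shift, either direction | N = 50 | N = 58 |
|---|---|---|
| 0 | 5% | 5% |
| 0.25 | 13% | 15% |
| 0.5 | 40% | 46% |

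If there is a true 1-point effect and the shift runs against it, power at N = 50 falls from about 92% to about 72% (0.25 point) or 39% (0.5 point). A larger sample does not remove the bias. In the table, the false rejection rate rises with N.

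**The case against.** The strongest reply is that the declared endpoints do not use the baseline. Section 1.0 defines the primary and secondary endpoints between cannabinoid and placebo sessions, and section 9.1 compares the three products. Step 3 shows that a baseline shift cancels there. This stands in full and sets the limit of the point.

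Four further replies carry weight:

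- **The link to the VAS is not stated.** The documents do not say that the single-question VAS is part of the MEFA, and the daily survey is not scheduled at Baseline. The point reaches the powered test only if the baseline VAS is taken with the MEFA. That is a reasonable reading, since the MEFA is the only outcome questionnaire scheduled at Baseline, but it remains an assumption.
- **Own use at baseline is allowed, not shown.** Familiarity with cannabis and tolerance of 5 mg THC do not require current use, and substance abuse disorders are excluded. The bias could be negligible.
- **Product use days are not all THC-free.** The Study Product contains 5 mg THC (6.1), and the THC-Only Product contains THC by name. For THC, participants on those products exchange own use for study THC. What differs from baseline is therefore background use, and it is not simply abstaining.
- **The MEFA recall period is not given.** Each period may last 7 days with only three sessions, and own use on the other days is not restricted. If recall spans the period, both sides include unrestricted days. The mismatch shrinks, and so does the benefit of controlling a single baseline day.

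One reply helps only in part. Cannabis use at screening (6.1) and alcohol use (9.4) are collected and can enter models. They describe the person and do not show whether the baseline answers followed own use that day.

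**Conclusion.** The point holds for change from baseline only. As written, the eligibility rules place the Baseline MEFA and the later MEFAs under different background conditions, and no other provision corrects this. The exploratory MEFA changes are exposed. So is the powered test in section 9.6, on the assumption that its baseline VAS accompanies the MEFA.

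Size and direction cannot be derived from the documents, and zero is possible. The 13% and 40% rejection rates are illustrations for assumed shifts of 0.25 and 0.5 point at N = 50 and SD 2, and are not estimates.

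A reader might infer that every change from baseline is contaminated, or that the primary result is invalid. The documents support neither reading. They permit own use at baseline without showing that it occurs, and the between-product endpoints in section 1.0 stand because the baseline cancels. The stated power is not in dispute as arithmetic. The change is worth making because it costs very little and the exposed comparison is the one that section 9.6 powers.

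**What to change.** Schedule the Baseline MEFA, and any baseline VAS, on the first product use day before the first product is taken. The existing wording of Inclusions 9 and 10 then covers it without amendment. Alternatively, extend that wording to the day of the Baseline MEFA.

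In either case:

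- Record same-day THC and alcohol use at the Baseline assessment, so that any remaining difference can be examined.
- State the MEFA recall period, since it determines how much a single controlled day achieves.
- Add to section 9.6 that change from baseline will not be attributed to a product without the contrast against placebo.

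The cost is an app scheduling change under the first option, or one more abstention day under the second, plus a short addition to the protocol text. No sample-size input changes, so N and the stated power are unaffected.
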